## **5.6 Packaging**

The bottles will be prepared and dispensed by the Research Pharmacy with appropriate labeling to include a statement that these products are *for investigational use only*.

## **5.7 Receiving, Storage, Dispensing, and Return**

### **5.7.1 Receipt of Drug Supplies**

The investigational products for this study will be delivered to and managed by the Research Pharmacy according to their established standard procedures.

### **5.7.2 Storage**

Investigational products should be stored 2-8°C.

### **5.7.3 Dispensing of Study Drug**

The study drug is to be used exclusively in the clinical study according to the instructions of this protocol and directions for use. The CRTU nurse is responsible for providing subjects with the study drug and instructions for dosing and proper storage of the study drug. They will record the amount of study drug dispensed, date of dispensing, as well as the amount of drug returned and drug remaining.

### **5.7.4 Return or Destruction of Study Drug**

At the completion of the study, there will be a final reconciliation of drug shipped, drug dispensed, drug returns, and drug remaining. This reconciliation will be logged on the drug reconciliation form, signed, and dated. Any discrepancies noted will be documented and investigated, prior to return or destruction of unused study drug. Drug destroyed on site will be documented in the study files.

## **6 Study Procedures**

A tabulated summary of all visits and assessments described in the following sections is provided in Table 1, Schedule of Events. To the extent possible, subjects will be expected to adhere to the established visit schedule.

After discussing the study with the investigator/appropriate study staff and after agreeing to study participation by signing the informed consent, subjects will be assigned a subject number. For any subject, it is the responsibility of the investigator or study team member to obtain written informed consent (subject's signature) prior to performing protocol-mandated assessments.

However, assessments performed as part of the routine care of the subject may be used to assess eligibility. The subject number will identify the subject throughout the duration of the study.

**Table 1: Schedule of Events**

	Screening	Treatment Period				Post-Treatment Follow-up		Post Study Follow-up
Time (Days)	Day -14 to Day 0	Day 0	Day 1	Day 29	Day 30	Day 45	Day 60 (Month 2)	Day 180 (Month 6, remote visit)
Visit	1	2A	2B	3A	3B	4	5	6
Visit window				±2 days		± 5 days	± 5 days	± 14 days
Informed Consent	x							
Inclusion/Exclusion Criteria	x	x		x				
Demographic Information	x							
Medical History	x	x		x			x	x
Weight & Height	x							
Vital signs		x		x			x	
Concomitant medications		x		x			x	x
Katz-Stirrat Diagram	x							
Boston CTS (BCTQ) Questionnaire		x		x			x	x
Hand Examination		x		x			x	
Hand/Wrist Pain & Interference VAS		x		x			x	x
Screening Labs 	x							
Safety Labs 				x 		x	x	
Pregnancy test, if applicable	x 	x 		x 			x 	
Urine 		x		x			x	
Peripheral blood 		x		x			x	
Study agent dosing		x	x	x	x			
AE Assessment		x		x			x	x

Complete Blood Count (CBC) with differential (hemoglobin, hematocrit, erythrocytes, mean corpuscular volume (MCV), red blood cell (RBC) distribution width, leukocytes, neutrophils, lymphocytes, monocytes, eosinophils, basophils, platelet count), Comprehensive Metabolic Panel (CMP) (potassium, sodium, chloride, bicarbonate, anion gap, blood urea nitrogen (BUN), creatinine, eGFR, calcium, glucose (plasma or serum), total protein, albumin, aspartate aminotransferase (AST), alkaline phosphatase (ALP), alanine aminotransferase (ALT), and total bilirubin), cystatin C, Hemoglobin A1c, C-Reactive Protein (CRP) and ESR.

Urine for Inflammation and Senescence Markers (to be stored- no testing)

Peripheral blood for Inflammation and Senescence Markers (done in [name] lab)

Complete Blood Count (CBC) with differential (hemoglobin, hematocrit, erythrocytes, mean corpuscular volume (MCV), red blood cell (RBC) distribution width, leukocytes, neutrophils, lymphocytes, monocytes, eosinophils, basophils, platelet count), Comprehensive Metabolic Panel (CMP) (potassium, sodium, chloride, bicarbonate, anion gap, blood urea nitrogen (BUN), creatinine, eGFR, calcium, glucose (plasma or serum), total protein, albumin, aspartate aminotransferase (AST), alkaline phosphatase (ALP), alanine aminotransferase (ALT), and total bilirubin), cystatin C, Hemoglobin A1c, C-Reactive Protein (CRP) and ESR.

Serum pregnancy test (if applicable)

Urine pregnancy test (if applicable), POC

 Safety labs can be performed at any Mayo Clinic site, up to 5 days before the 3A appt

## 6.1 Visit 1, Screening

Subjects will be invited to participate, review, and sign the consent form. This visit may be performed remotely, using video or phone visit options and the consent form may be signed using remote consent technology consistent with institutional standards.

Eligibility data will include screening blood tests, pregnancy test if applicable, review of medications and medical history, demographic information, Katz-Stirrat hand diagram, and weight and height. Subjects will be informed of the contraceptive protocol and potential interactions, and we will record their compliance with these restrictions. Blood for screening and safety tests will be collected either in Rochester or at another Mayo Clinic site more convenient to the potential subject's home. Subjects will be notified via phone, email, or patient portal contact if they pass the eligibility protocol and will schedule their 2A visit.

## 6.2 Visit 2A, Baseline, Day 0

Subjects will have their vital signs measured and review their medical history and concomitant medications with the CTRU nurse to ensure they continue to meet inclusion/exclusion criteria. Women of child bearing potential will confirm their pregnancy status via a point of care pregnancy test. The study team will administer the hand examination including measurement of pinch and grip strength and record the information into REDCap. The subject will fill out hand/wrist pain VAS and hand/wrist interference VAS assessments and the Boston CTS (BCTQ) questionnaire in REDCap. The subject will provide a blood and urine sample for inflammation and senescence markers. Finally, the CTRU nurse will administer the first IP dose and provide the subject with IP for the following day (20 mg/kg/day).

## 6.3 Visit 2B, Day 1

The 2nd IP administration will occur on Day 1 (12 -36 hours after the 1st IP administration). This dosing will occur at the subject's home. The subject will be instructed at the baseline visit to complete the Drug Diary and return it and the bottle along with any unused study drug.

## 6.4 Visit 3A, Day 29 ( $\pm 2$ days)

Blood for safety tests will be collected either in Rochester or at another Mayo Clinic site more convenient to the research subject's home within 5 days prior to the scheduled appt on day 29. These results will be reviewed prior to the third IP dose, to confirm there are no clinically significant changes. On day 29, subjects will return to Mayo Clinic's Clinical Trial Research Unit (CTRU). Subjects will have their vital signs measured and review changes to their medical history and concomitant medications with the CTRU nurse to ensure they continue to meet inclusion/exclusion criteria. Women of child bearing potential will confirm their pregnancy status via a point of care pregnancy test. The study team will administer the hand examination including measurement of pinch and grip strength and record the information into REDCap, record adverse events, and collect the Subject Drug Diary. The subject will fill out hand/wrist pain VAS and hand/wrist interference VAS assessments and the Boston CTS (BCTQ) questionnaire in REDCap. The subject will provide a blood and urine sample for inflammation and senescence markers. Finally, the CTRU nurse will administer the third IP dose and provide the subject with IP for the following day (20 mg/kg/day).

## **6.5 Visit 3B, Day 30 (±2 days)**

The 4th IP administration will occur on Day 30 (12 -36 hours after the 3rd IP administration). This dosing will occur at the subject's home. The subject will be instructed at the baseline visit to complete a Drug Diary and return it and the bottle along with any unused study drug.

## **6.6 Visit 4, Day 45 (±5 days)**

At the 45-day visit, blood for safety tests will be collected either in Rochester or at another Mayo Clinic site more convenient to the research subject's home. At this point the study intervention is completed, and subject will enter the post-treatment follow-up phase.

## **6.7 Visit 5, Day 60 (±5 days)**

At the 60-day visit, subjects will return to Mayo Clinic's Clinical Trial Research Unit (CTRU). Subjects will have their vital signs measured and review changes to their medical history and concomitant medications with the CTRU nurse. Women of childbearing potential will confirm their pregnancy status via a point of care pregnancy test. The subject will provide a blood and urine sample for inflammation and senescence markers as well as safety labs. The study team will administer the hand examination and record the information into REDCAP. The subject will fill out hand/wrist pain VAS and hand/wrist interference VAS assessments and the Boston CTS (BCTQ) questionnaire in REDCap. The study team will record adverse events and collect the Subject Drug Diary.

## **6.8 Visit 6, Day 180 (remote visit) (±14 days)**

At day 180, subjects will be contacted by phone and email. The study coordinator will assess the subject for Adverse Events, and record answers to the hand/wrist pain VAS, hand/wrist interference VAS, the BCTQ questionnaire, changes to medical history, and concomitant drugs into REDCap. Alternately, the subject can answer the hand/wrist pain VAS, hand/wrist interference VAS, the BCTQ questionnaire directly through the links sent via email.

## **6.9 Assessments/Procedures**

### **6.9.1 Demographic Information**

The following elements of demographic information will be collected at Day 0: date of birth, age, race, ethnicity, biological sex, phone number, email address, and physical address.

### **6.9.2 Medical History/Prior and Concomitant Medications**

Medical history will be obtained preliminarily from subject medical records with incomplete entries to be completed during the screening visit by subject recall. At subsequent visits, the CTRU nurse will record medical history and concomitant medications. Medication history will include current medications only. The subject will also be questioned on their tobacco and caffeine usage.

### **6.9.3 Vital Signs**

Weight and height will be recorded at Screening; Vital signs will be collected at all subsequent in person visits. These measurements include heart rate, respiratory rate, temperature, blood pressure, and body weight.

### **6.9.4 Hand Examination**

The study coordinator will measure pinch and grip strength of each hand, and record hand dominance.

#### **6.9.5 Subject Questionnaires, Assessments, and Diagrams**

The subject will complete a Katz-Stirrat Hand Diagram during screening. The subject will complete VAS hand pain and VAS pain interference assessments and the Boston CTS Questionnaire (BCTQ) at Day 0, 30, 60, and 180. The context is symptoms of the study hand at the time of test administration.

#### **6.9.6 Screening Labs**

Screening labs will be collected within 14 days prior to Day 0: Complete Blood Count (CBC) with differential (hemoglobin, hematocrit, erythrocytes, mean corpuscular volume (MCV), red blood cell (RBC) distribution width, leukocytes, neutrophils, lymphocytes, monocytes, eosinophils, basophils, platelet count), Comprehensive Metabolic Panel (CMP) (potassium, sodium, chloride, bicarbonate, anion gap, blood urea nitrogen (BUN), creatinine, eGFR, calcium, glucose (plasma or serum), total protein, albumin, aspartate aminotransferase (AST), alkaline phosphatase (ALP), alanine aminotransferase (ALT), and total bilirubin), cystatin C, Hemoglobin A1c, C-Reactive Protein (CRP) and ESR.

#### **6.9.7 Safety Labs**

Safety labs will be collected on days 29, 45, and 60: Complete Blood Count (CBC) with differential (hemoglobin, hematocrit, erythrocytes, mean corpuscular volume (MCV), red blood cell (RBC) distribution width, leukocytes, neutrophils, lymphocytes, monocytes, eosinophils, basophils, platelet count), Comprehensive Metabolic Panel (CMP) (potassium, sodium, chloride, bicarbonate, anion gap, blood urea nitrogen (BUN), creatinine, eGFR, calcium, glucose (plasma or serum), total protein, albumin, aspartate aminotransferase (AST), alkaline phosphatase (ALP), alanine aminotransferase (ALT), total bilirubin), cystatin C, Hemoglobin A1c, C-Reactive Protein (CRP) and ESR.

#### **6.9.8 Labs for Research (Urine and Peripheral Blood)**

At days 0, 29, and 60, 40 ml of blood and 40 ml of urine will be collected to measure blood for inflammation and senescence markers.

#### **6.9.9 Pregnancy Testing**

Pregnancy testing will be required for female participants of childbearing potential (see Appendix A) and all premenarchal female participants during this study. A serum pregnancy test will be obtained at screening. Urine pregnancy tests (POC) will be performed at Day 1 and Day 29 prior to administration of study drug, and at day 60.

If the investigator is notified of a pregnancy (confirmed by a serum pregnancy test), see Section 8.4 for reporting requirements both during the study and 30 days (female participants of childbearing potential) after the last dose of study drug.

#### **6.9.10 Contraceptive Compliance**

All female participants of childbearing potential will be required to record their compliance with the contraceptive measures listed in Appendix 1, in accordance with the Clinical Trials Facilitation

and Coordination Group recommendations. Men, women not of childbearing potential, and women who are not sexually active with opposite sex partners will not be required to record contraceptive measures.

### 6.9.11 Interaction Compliance

All participants will be questioned regarding their alcohol and caffeine usage and will record their compliance to reduce their consumption, if needed, based on the study protocol.

## 7 Statistical Plan

### 7.1 Sample Size Determination

Using data from a previous study from a similar study population (Schrier *et al*, Ultrasound in Medicine and Biology, 46:2236-44, 2020), the variability (SD) of a 3-month change of the Boston Carpal Tunnel Questionnaire (BCTQ) subscores (symptom severity score SSS, functional severity score FSS) was approximately 0.7. With 40 subjects, the minimum detectable change in the mean value is 0.3/0.4 with 80%/90% power and a significance level of 0.05 based on a paired t-test. Given that the desired detectable difference is 1.0, there should be sufficient power to detect that difference. For the secondary goal of detecting differences between males and females, assuming 20 subjects per group the minimum detectable difference is 0.6/0.7 with 80%/90% power. Thus, the study will have sufficient power to detect large group differences.

### 7.2 Statistical Methods

#### Descriptive Statistics

The data will be summarized using standard statistics including the mean, median, and standard deviation at each visit. Graphical displays of the data (scatterplots, boxplots) will also be used.

#### Handling of Missing Data

Basic summaries of subject demographics and baseline BCTQ will be run for subjects who drop out prior to completion of the study *vs.* those who completed the 60-day portion of the study.

#### Primary Hypothesis:

The primary hypothesis is that the BCTQ score will improve by 1 point from pre-treatment to 60 days post-treatment. Confidence intervals of the change in score, along with paired t-tests will be run, however the focus will be on the confidence intervals. Mixed effects models including all BCTQ measurements will be used as a secondary analysis. Additional exploration comparing the BCTQ changes between males and females will be made using a two-sample t-test. Similar analyses will be run using the SASP markers.

#### Secondary Hypotheses:

There are two secondary hypotheses. The first secondary hypothesis is that clinical improvement will be proportional to the effect in reducing blood markers of cellular senescence. Analysis will

include correlations between baseline SASP markers and the BCTQ score and between the change in SASP markers and the change in BCTQ. The second secondary hypothesis is that the symptomatic changes noted on the BCTQ at 2 months will be maintained at 6 months.

## Interim Analysis

No interim analysis is planned.

### 7.3 Subject Population(s) for Analysis

As a pilot study, all subjects who complete the 60-day study visit ( $60 \pm 5$  days) will be the main population of interest, though summaries will be made of those who do not reach that point.

## 8 Safety and Adverse Events

Safety evaluations will include adverse event (AE) and serious AE (SAE) reporting. Adverse event reporting will be conducted throughout the study for all subjects. The reporting period begins at administration of IP (Day 0) and continues through the post treatment follow-up period, –Day 180). Adverse events will be assessed at Day 0, 29,, 60, and 180. Subjects will be encouraged to contact the Primary Investigator or study coordinator immediately if they experience any AE or SAE's during the study.

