### 4.4 Early Withdrawal of Subjects

#### 4.4.1 When and How to Withdraw Subjects

All subjects will be assessed during the 2 days of medication administration, subsequent days of medication administration, and all study visits. If a severe adverse event (SAE) occurs at any time during administration of the 2-day drug regimen, a formal review will occur, and subsequent patients will be enrolled one at a time using the same regimen. If three or more events accrue, the pilot study will be held and either a potential dosing regimen revisited, or discontinuation of the study protocol will occur. Other interventions will be at the direction of the Food and Drug Administration and Mayo Institutional Review Board.

Patients may also wish to withdraw if they perceive that their symptoms of carpal tunnel syndrome are not improving, and they wish additional treatment such as surgery or a steroid injection. If they are tolerating the Fisetin otherwise, we will request that they continue the Fisetin in addition to the other treatments, and such patients will continue to be followed, but will be excluded from the final analysis. We aim to continue enrollment until 40 patients complete the 60-day trial time point without intervening treatment for their CTS.

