## **5.2 Treatment Regimen**

The treatment dosing regimen is based on the preclinical information available about Fisetin along with information about similar clinical drug trials using the alternative senolytic compounds Dasatinib and Quercetin. Participants will be administered Fisetin over a two-day course of treatment twice during the study duration. Each day subjects will receive a target dose of 20 mg/kg of body weight. Therefore, for an adult with a body weight of 75 kg, each day the participant will take 15 of the 100 mg capsules. Dosing should be completed in as short of a time as possible, with a goal of 10 minutes and a maximum time of 60 minutes to complete ingestion of the capsules. Subjects can empty the capsules into room temperature or cold drinks or puddings, such as milk, yoghourt, or apple sauce, if they are unable or unwilling to ingest multiple capsules. The drink or pudding will be consumed within 10 to 60 minutes. By mass spectrometry, we verified that Fisetin is stable under these conditions. Dosing will occur at days 0 and 1 and repeated at days 29 and 30.

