## **8.2 Recording of Adverse Events**

At each contact with the subject, the study team must seek information on adverse events by specific questioning and, as appropriate, by examination. Information on all adverse events should be recorded immediately in the source document, and also in the appropriate adverse event section of the case report form (CRF) or in a separate adverse event worksheet. All clearly related signs, symptoms, and abnormal diagnostic, laboratory, or procedure results should be recorded in the source document.

All adverse events occurring during the study period must be recorded. The clinical course of each event should be followed until resolution, stabilization, or until it has been ultimately determined that the study treatment or participation is not the probable cause. Serious adverse events that are still ongoing at the end of the study period must be followed up, to determine the final outcome. Any serious adverse event that occurs during the Adverse Event Reporting Period and is considered to be at least possibly related to the study treatment or study participation should be recorded and reported immediately.

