## 8.5 Stopping Rules

All subjects will be assessed during the 2 cycles each lasting for 2 days of Fisetin administration (after Visits 1 and 2; total 4 days) and during each visit following administration of the first cycle of drugs. If a severe adverse event occurs at any time during administration of the 2-day drug regimen, the study will pause, and a formal review will occur. Subsequent subjects will only be enrolled if the SAE is determined to be unrelated to the study drug. Other interventions will be as according to the direction of the FDA and Mayo IRB.

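### No adverse-event assessment is scheduled on Days 1, 30 or 45, although Sections 4.4.1 and 8.5 say subjects are assessed on every dosing day and at later visits

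*Combined protocol and SAP*

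**What the plan says.** Section 8 sets the AE calendar: "Adverse events will be assessed at Day 0, 29,, 60, and 180". The "AE Assessment" row of Table 1 carries four marks which, read with the column order and Section 8, fall on the same four days.

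Treatment is given on four days. Section 5.2 says: "Dosing will occur at days 0 and 1 and repeated at days 29 and 30". The Day 0 and Day 29 doses are given in the clinic. For Day 1, Section 6.3 says: "This dosing will occur at the subject's home. The subject will be instructed at the baseline visit to complete the Drug Diary". Section 6.5 says nearly the same for Day 30. Neither section describes any staff contact, and Section 5.4 gives the diary's purpose as documenting compliance. For Day 45, Section 6.6 says "blood for safety tests will be collected either in Rochester or at another Mayo Clinic site" and mentions no AE questions.

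Three other sections ask for more than this calendar provides:

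- Section 4.4.1: "All subjects will be assessed during the 2 days of medication administration, subsequent days of medication administration, and all study visits".
- Section 8.5: "All subjects will be assessed during the 2 cycles each lasting for 2 days of Fisetin administration", to which it adds each visit after the first cycle.
- Section 8.2: "At each contact with the subject, the study team must seek information on adverse events by specific questioning".

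**The concern.** Sections 4.4.1 and 8.5 both place the assessment statement directly before a rule on severe events during a 2-day course. In Section 8.5 such an event pauses the study for formal review. That rule works best when the study team hears of an event promptly, yet the second day of each course is taken at home on a day with no scheduled questioning. There is no formal DSMB (Section 8.6.1), so the principal investigator depends on the AE information that the schedule produces.

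AE monitoring is also one of the safety endpoints in Section 3.6. If the next scheduled question comes about a month after a home dose, short-lived reactions reach the dataset only through recall or a spontaneous call.

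**Working it through.** **Step 1. Compare the calendars.**

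| Visit (day) | Dose | AE assessment in Section 8 and Table 1 | Assessment stated in 4.4.1 and 8.5 |
|---|---|---|---|
| 2A (0) | clinic | yes | yes |
| 2B (1) | home | no | yes, dosing day |
| 3A (29) | clinic | yes | yes |
| 3B (30) | home | no | yes, dosing day |
| 4 (45) | none | no | yes, later visit |
| 5 (60) | none | yes | yes, later visit |
| 6 (180) | none | yes | yes, later visit |

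AE assessment is scheduled on 2 of 4 dosing days and at 4 of the 7 visits from Day 0 on. The missing days are 1, 30 and 45.

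**Step 2. Apply Section 8.2 separately.** It covers contacts with the subject. No contact is described on Days 1 and 30, so 8.2 is not contradicted there. At Day 45, if the blood draw counts as a contact, 8.2 requires AE questions that Table 1 and Section 6.6 do not show.

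**Step 3. Time from home dose to the next scheduled AE question.** The windows are ±2 days for Days 29 and 30 and ±5 days for Days 45 and 60 (Sections 6.4 to 6.7).

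- Day 1 to Day 29: 29 − 1 = 28 days. Range: 27 − 1 = 26 to 31 − 1 = 30.
- Day 30 to Day 60: 60 − 30 = 30 days. Range: 55 − 32 = 23 to 65 − 28 = 37.
- Day 45 falls 45 − 30 = 15 days after the last dose. Range: 40 − 32 = 8 to 50 − 28 = 22.

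**Step 4. New subjects who could start treatment in a 28-day gap.** The documents give 40 subjects and a 2-year study but no accrual rate, so an even rate is assumed. With 365/12 = 30.4 days per month, the number is (40 / months of accrual) × (28 / 30.4).

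- 24 months: 1.67 × 0.921 = 1.5.
- 18 months (2 years less 6 months of follow-up): 2.22 × 0.921 = 2.0.
- 12 months: 3.33 × 0.921 = 3.1.

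This number matters only if a severe event follows a home dose and the subject does not report it.

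**The case against.** The strongest reply is that the plan already has other routes for detecting events. Section 8 runs AE reporting from Day 0 to Day 180 and encourages subjects to contact the investigator or coordinator at once about any AE. Staff record AEs and collect the diary at Day 29 (Section 6.4) and Day 60 (Section 6.7). Safety labs are reviewed before the third dose. Under the abnormal laboratory values heading of Section 8.1, a laboratory value that worsens to outside the normal range is documented as an AE and prompts follow-up such as a repeat test or a telephone call. The termination rule in Section 8.5 is not limited to dosing days. How often to question subjects between visits is partly a design choice.

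Most of this stands, and it rules out three stronger readings that a reader might take from the calendar:

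- *Reactions to the home doses are never asked about.* They are, at Days 29 and 60. The issue is delay.
- *The pause rule cannot act on Day 1 or Day 30.* It can act on a self-reported event. On those days it relies on self-report.
- *AE incidence is under-counted.* Late questioning may lose transient events, but the documents contain no figure on recall loss, so neither the fact nor the size can be asserted.

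The reply does not remove the contradiction. Self-report is encouragement and not an assessment, whereas 4.4.1 and 8.5 state that subjects are assessed. Self-report may also be incomplete for events that a subject thinks minor: Section 8.3.1 grades as severe any problem needing more than one day of over-the-counter medication. Laboratory tests do not capture symptoms. The diary form is not in the documents, so whether it has AE fields is unknown.

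**Conclusion.** The point holds as an internal inconsistency with a practical consequence. Section 8 and Table 1 omit Days 1, 30 and 45. Sections 4.4.1 and 8.5 include them, and Section 8.2 adds Day 45 if the draw is a contact. The first scheduled questioning comes 28 days (26 to 30) after the Day 1 dose and 30 days (23 to 37) after the Day 30 dose, with self-report and safety labs in between. The pause under Section 8.5 may be triggered late, and transient events depend on recall.

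The figure of about 1.5 to 3 further subjects dosed in a 28-day gap is illustrative. It assumes even accrual of 40 subjects over 24 to 12 months and a severe event that is not self-reported. The conclusion also takes the assessments in 4.4.1 and 8.5 to include asking about AEs. The word is not defined there, but the severe-event rule that follows makes this the natural reading. The inconsistency should be corrected, but it does not show that safety monitoring is absent.

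**What to change.** Reconcile Table 1, Section 8 and Sections 6.3, 6.5 and 6.6 with Sections 4.4.1, 8.2 and 8.5, so that one AE schedule governs. State whether the Day 45 draw counts as a contact under 8.2.

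If the assessments stated in 4.4.1 and 8.5 are kept:

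- Mark AE assessment at Visits 2B, 3B and 4 in Table 1, and list those days in Section 8.
- Put AE items in the existing Drug Diary and add a brief call or portal message after each home dose. The diary alone would help recall but not timeliness, because it is collected only at Days 29 and 60.
- Ask AE questions with the Day 45 labs, by phone or portal when the draw is at another site.

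The cost is a text and table edit, a few diary items and up to three short contacts per subject. No new visit or procedure is needed.
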